## **3. PARTICIPANT SELECTION**

Eligibility tests for subjects must be completed within 42 days prior enrollment, unless otherwise stated.

### 3.1 Inclusion Criteria

- 3.1.1 Previously untreated stage IA, IB, IIA, or IIB classical Hodgkin Lymphoma
- 3.1.2 Non-bulky disease defined as less than 10 cm in maximal diameter
- 3.1.3 Measurable disease  $\geq 1.5$  cm as measured on PET-CT
- 3.1.4 Age  $\geq 18$
- 3.1.5 ECOG performance status 0-2 (see Appendix B)
- 3.1.6 Participants must have initial organ and marrow function as defined below:
  - Absolute neutrophil count  $\geq 1,000/\text{mcL}$
  - Platelets  $\geq 100,000/\text{mcL}$
  - Total bilirubin  $\leq 2$ , unless due to Gilbert's disease
  - AST (SGOT)/ALT (SGPT)  $\leq 2.5$  X institutional upper limit of normal
  - Creatinine clearance  $\geq 30$  mL/min
- 3.1.7 LVEF by echocardiogram or MUGA within institutional normal limits
- 3.1.8 Participant must be willing to use two effective forms of birth control during protocol therapy. Men and women must continue using two effective forms of birth control for 6 months following treatment.
- 3.1.9 Ability to understand and the willingness to sign a written informed consent document

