### 3.2 Exclusion Criteria

- 3.2.1 Participants who have had prior cHL-directed chemotherapy or radiotherapy
- 3.2.2 Participants receiving any other investigational agents
- 3.2.3 Participants with known CNS involvement of lymphoma
- 3.2.4 History of allergic reactions attributed to compounds of similar chemical or biologic composition to Adriamycin, Dacarbazine, or brentuximab
- 3.2.5 Pre-existing grade 2 or greater neuropathy
- 3.2.6 Uncontrolled intercurrent illness including, but not limited to ongoing or active infection, symptomatic congestive heart failure, unstable angina pectoris, cardiac arrhythmia, or psychiatric illness/social situations that would limit compliance with study requirements
- 3.2.7 Pregnant women are excluded from this study because brentuximab is an antibody drug conjugate with a linked potent anti-tubule agent with the potential for teratogenic or abortifacient effects. Because there is an unknown but potential risk of adverse events in nursing infants secondary to treatment of the mother with brentuximab, breastfeeding should be discontinued if the mother is treated with brentuximab. These potential risks may also apply to other agents used in this study.
- 3.2.8 Participants with a history of a different malignancy are ineligible unless they have been disease free for 1 year and considered at low risk for relapse, except for: cervical cancer in situ, ductal carcinoma in situ, localized prostate cancer with

no detectable disease by imaging studies, and non-melanoma cancers of the skin, which are eligible at any time.

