3.2.9 Known HIV positivity

**3.3 Inclusion of Women, Minorities and Other Underrepresented Populations**

There is no evidence to suggest that the outcome will differ by gender or ethnicity. Given the small size of our study there is insufficient power to detect small effects in these groups. There is no plan to exclude women, minorities or underrepresented populations and they will be able to participate if eligibility criteria are met.

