### 6.2.4 Hepatic Dysfunction

LFT's should be checked on the day of or day prior to treatment. No dose modification required for total bilirubin less than 1.5 mg/dL. Participants with total bilirubin of 1.5 to 2.0 mg/dL at study entry (and not due to Gilbert's disease) will be initiated at a 50% dose reduction of Adriamycin. For total bilirubin greater than 1.5 mg/dL on day 1 or 15, Adriamycin will be administered as below. Brentuximab vedotin will be held for ≥ grade 3 bilirubin (>3 mg/dL) until toxicity is ≤ grade 2. Upon restarting, the brentuximab dose will be reduced to 0.8 mg/kg. If a second dose reduction is required, dose will be reduced to 0.6 mg/kg. There are no dose reductions for dacarbazine based on bilirubin.

Total Bilirubin (mg/dL)	% Brentuximab Dose	% Adriamycin Dose	% Dacarbazine Dose
<1.5	100%	100%	100%
1.5 – 3.0	100%	50%	100%
>3.0-5.0	0%	25%	100%
>5.0	0%	0%	100%

CONFIDENTIAL

This document is confidential. Do not disclose or use except as authorized.

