## **8. STUDY CALENDAR**

### **8.1 Pre-Treatment Evaluations:** To be completed within 42 days prior to enrollment unless otherwise specified:

- Signed inform consent
- Vital signs, including temperature, blood pressure, heart rate, and respiratory rate
- Complete physical examination, including height and weight
- Medical history: Detailed documentation of disease and treatment history with outcomes
- ECOG performance status
- Concurrent medical conditions, including peripheral neuropathy
- Concurrent medications
- CBC with differential
- Erythrocyte sedimentation rate (ESR)
- Serum chemistries: Electrolytes (sodium, potassium, chloride, and CO2), calcium, magnesium, phosphate, blood urea nitrogen (BUN), creatinine, glucose, and liver function tests (aspartate aminotransferase (AST) and alanine aminotransferase (ALT), alkaline phosphatase (ALP), total protein, albumin, and total bilirubin
- Coagulation studies including prothrombin time (PT), partial thromboplastin time (PTT) and international normalized ratio (INR)
- Hepatitis B serology testing (Hepatitis B core antibody, Hepatitis B surface antigen, Hepatitis B surface antibody) (may be performed within 6 months prior to start of study treatment)
- Baseline EKG
- Echocardiogram or MUGA to determine LVEF
- Full-body PET-CT scan (neck, chest, abdomen/pelvis). Tumor measurements will be centrally performed by the DF/HCC tumor imaging metric core (TIMC)

- Assessment of Early Favorable or Early Unfavorable based on GHSG criteria (see footnote 1 in required data table)
- Serum pregnancy test for women of childbearing potential must be performed within 7 days

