## USE IN SPECIFIC POPULATIONS

Moderate or severe hepatic impairment or severe renal impairment: MMAE exposure and adverse reactions are increased. Avoid use (5.6, 5.7, 8.6, 8.7).

See 17 for PATIENT COUNSELING INFORMATION.

Revised: 02/2015

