**Table 1: Recommended ADCETRIS Dosage**

	Recommended Starting Dosage
Normal renal and hepatic function	1.8 mg/kg up to 180 mg
Renal impairment	
Mild (creatinine clearance >50–80 mL/min) or moderate (creatinine clearance 30–50 mL/min)	1.8 mg/kg up to 180 mg
Severe (creatinine clearance less than 30 mL/min)	Avoid use [see Warnings and Precautions (5.6) ]
Hepatic impairment	
Mild (Child-Pugh A)	1.2 mg/kg up to 120 mg
Moderate (Child-Pugh B) or severe (Child-Pugh C)	Avoid use [see Warnings and Precautions (5.7) ]

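### Eligibility does not exclude known Child-Pugh B or C liver impairment, in which the appended brentuximab label says to avoid the drug, although it does carry the label's matching renal limit

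*Combined protocol and SAP*

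**What the plan says.** Section 3.1.6 ("Participants must have initial organ and marrow function as defined below") requires ANC of at least 1,000/mcL, platelets of at least 100,000/mcL, total bilirubin no higher than 2 unless explained by Gilbert's disease, AST/ALT no higher than 2.5 times the institutional upper limit, and creatinine clearance of at least 30 mL/min.

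None of the nine exclusions, 3.2.1 to 3.2.9, names liver disease, cirrhosis or a Child-Pugh class. The nearest is 3.2.6: "Uncontrolled intercurrent illness including, but not limited to ongoing or active infection, symptomatic congestive heart failure" and further examples, none of them hepatic.

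Section 6.2.4 deals with hepatic dysfunction through bilirubin alone. "Participants with total bilirubin of 1.5 to 2.0 mg/dL at study entry" that is not due to Gilbert's disease start Adriamycin at half dose. The table there keeps brentuximab at 100% for bilirubin of 1.5 to 3.0 mg/dL and holds it only above 3 mg/dL.

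The Adcetris prescribing information bound into the same file says, in its highlights: "Moderate or severe hepatic impairment or severe renal impairment: MMAE exposure and adverse reactions are increased. Avoid use". Its Table 1 and sections 5.7 and 8.7 repeat the hepatic advice for Child-Pugh B and C. Table 1 and sections 5.6 and 8.6 repeat the renal advice for creatinine clearance below 30 mL/min.

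**The concern.** The label gives two avoid-use warnings side by side. The renal one has an exact counterpart in the eligibility criteria. The hepatic one does not: the protocol uses laboratory cut-offs, which are not the classification the label uses, and it does not say that it means to depart from the label here.

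At stake is the safety of an individual participant. Someone with known, stable class B disease whose laboratory values fell within 3.1.6 could be enrolled and given full-dose brentuximab at 1.2 mg/kg, together with doxorubicin and dacarbazine. The label's section 5.8 adds that pre-existing liver disease may raise the risk of hepatotoxicity, that some cases were fatal, and that some followed the first dose. Checking liver tests during treatment therefore does not fully replace an entry exclusion.

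**Working it through.** The plan states no figure on this point, so the check compares texts and then looks at the label's data.

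**Comparison of the two warnings**

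| | Severe renal impairment | Moderate or severe hepatic impairment |
|---|---|---|
| Label advice | Avoid if creatinine clearance is below 30 mL/min (5.6, 8.6, Table 1) | Avoid in Child-Pugh B or C (5.7, 8.7, Table 1) |
| Dose studied | 1.2 mg/kg | 1.2 mg/kg |
| MMAE AUC against normal function | about 2-fold | about 2.2-fold (cohort of 7: one class A, five class B, one class C) |
| Grade 3 or worse events | 3/3 against 3/8 | 6/6 (B and C) against 3/8 |
| Protocol eligibility | At least 30 mL/min (3.1.6) | No class limit; bilirubin and AST/ALT only (3.1.6) |

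**Strength of the label data**

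Class B count: five class B and one class C patient, 6/6 with reactions, so class B alone is 5/5.

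Exact (Clopper-Pearson) 95% intervals. For n events in n patients the lower limit is 0.025^(1/n) and the upper limit is 1:
- 6/6: 0.025^(1/6) = 0.541, so 54% to 100%
- 5/5: 0.025^(1/5) = 0.478, so 48% to 100%
- 3/3: 0.025^(1/3) = 0.292, so 29% to 100%
- 3/8: 8.5% to 75.5%

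Fisher exact, two-sided (sum of all tables no more probable than the one observed):
- B and C, 6/6 against 3/8: (84 + 9)/3003 = 0.031
- B alone, 5/5 against 3/8: (56 + 40 + 1)/1287 = 0.075
- Severe renal, 3/3 against 3/8: (20 + 10)/165 = 0.18

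The intervals overlap throughout. Still, the hepatic data are at least as strong as the renal data whose limit is already in 3.1.6, and they were obtained at this protocol's per-dose level.

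**Dose intensity**

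For mild (class A) impairment the label lowers the dose to 1.2 mg/kg every 3 weeks: 1.2/3 = 0.4 mg/kg per week. The protocol gives 1.2 mg/kg on days 1 and 15 of 28: 1.2/2 = 0.6 mg/kg per week. A class B patient would start at 0.6/0.4 = 1.5 times the weekly intensity the label recommends for class A.

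**Do other provisions close the gap?**
- Exclusion 3.2.6 reaches uncontrolled illness. It may cover decompensated liver disease but need not cover known, stable class B disease.
- Section 8.1 collects albumin and coagulation tests including INR, but no eligibility limit uses them.
- Section 6.2.4 adjusts only Adriamycin for a raised entry bilirubin.

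**Effect on the statistics**

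None. The section 13.1.1 rule of at least 31 complete responses in 34 gives an exact one-sided type I error of 0.0906 and power of 0.912 for 81% against 95%. These agree with the stated 0.09 and 91%, and the change proposed here leaves them as they are.

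**The case against.** The strongest reply is that no affected patient has been shown to exist. Such a person must be class B or C and also pass the bilirubin, AST/ALT, platelet and ANC limits. The documents do not set out Child-Pugh scoring, so how many would pass cannot be derived from them. The label's six patients come without laboratory values and may not resemble people already filtered by 3.1.6. This stands. It limits the size of the point and rules out any estimate of harm.

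A second reply is that the study runs under an IND and sets its own rules elsewhere. It gives full doses to afebrile patients with ANC below 500 (6.2.3), where the label holds for grade 3 or 4 neutropenia. It reduces the dose for grade 2 neuropathy (6.2.7), where the label holds. Laboratory limits for the liver could be a similar choice. But those two departures are written out as rules, whereas the protocol text never mentions Child-Pugh class.

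Third, there is partial cover. An investigator confirms eligibility, the Coordinating Center reviews source documents from outside sites, liver tests precede each dose, the monitoring committee reviews toxicity quarterly, and the label is in the same file. These make enrolment of such a patient less likely, but none of them makes the patient ineligible.

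Last, an exclusion limited to known disease leaves unclassified liver disease untouched. That is true. The proposal closes the plain gap and does not claim to do more.

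**Conclusion.** The omission is real and small. Section 3 has hepatic laboratory limits but no exclusion for known Child-Pugh B or C impairment, while the label's paired renal limit is present at its exact cut-off. The benefit of correcting it is individual patient safety; no claim is made about the rate of grade III and IV events as a secondary endpoint.

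The conclusion assumes that a patient with known class B disease could meet the 3.1.6 limits, which the documents neither show nor exclude. If none could, the added line would be redundant but harmless. The label's figures rest on six impaired and eight unimpaired patients, so they justify caution only. This is an inexpensive improvement for the sponsor to consider, held with medium confidence.

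**What to change.** Add to section 3.2: *3.2.10 Known moderate or severe (Child-Pugh B or C) hepatic impairment*, with a matching item on the eligibility checklist. Leave 3.1.6 and 6.2.4 as they are.

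The wording follows an existing pattern (for example 3.2.9, "Known HIV positivity"). It needs no new test, because section 8.1 already records "Concurrent medical conditions, including peripheral neuropathy". The cost is one line in an amendment and one checklist item, with negligible loss of accrual.

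If the sponsor instead intends to allow these patients, the protocol should say so and give the reason.

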### 3.2 Exclusion Criteria

- 3.2.1 Participants who have had prior cHL-directed chemotherapy or radiotherapy
- 3.2.2 Participants receiving any other investigational agents
- 3.2.3 Participants with known CNS involvement of lymphoma
- 3.2.4 History of allergic reactions attributed to compounds of similar chemical or biologic composition to Adriamycin, Dacarbazine, or brentuximab
- 3.2.5 Pre-existing grade 2 or greater neuropathy
- 3.2.6 Uncontrolled intercurrent illness including, but not limited to ongoing or active infection, symptomatic congestive heart failure, unstable angina pectoris, cardiac arrhythmia, or psychiatric illness/social situations that would limit compliance with study requirements
- 3.2.7 Pregnant women are excluded from this study because brentuximab is an antibody drug conjugate with a linked potent anti-tubule agent with the potential for teratogenic or abortifacient effects. Because there is an unknown but potential risk of adverse events in nursing infants secondary to treatment of the mother with brentuximab, breastfeeding should be discontinued if the mother is treated with brentuximab. These potential risks may also apply to other agents used in this study.
- 3.2.8 Participants with a history of a different malignancy are ineligible unless they have been disease free for 1 year and considered at low risk for relapse, except for: cervical cancer in situ, ductal carcinoma in situ, localized prostate cancer with

no detectable disease by imaging studies, and non-melanoma cancers of the skin, which are eligible at any time.

3.2.9 Known HIV positivity

**3.3 Inclusion of Women, Minorities and Other Underrepresented Populations**

There is no evidence to suggest that the outcome will differ by gender or ethnicity. Given the small size of our study there is insufficient power to detect small effects in these groups. There is no plan to exclude women, minorities or underrepresented populations and they will be able to participate if eligibility criteria are met.

**4. REGISTRATION PROCEDURES**

**4.1 General Guidelines for DF/HCC and DF/PCC Institutions**

Institutions will register eligible participants with the Clinical Trials Management System (CTMS) OnCore. Registration must occur prior to the initiation of protocol therapy. Any participant not registered to the protocol before protocol therapy begins will be considered ineligible and registration will be denied.

An investigator will confirm eligibility criteria and a member of the study team will complete the protocol-specific eligibility checklist.

Following registration, participants may begin protocol therapy. Issues that would cause treatment delays should be discussed with the Overall Principal Investigator (PI). If a participant does not receive protocol therapy following registration, the participant's registration on the study must be canceled. Registration cancellations must be made in OnCore as soon as possible.

**4.2 Registration Process for DF/HCC and DF/PCC Institutions**

DF/HCC Standard Operating Procedure for Human Subject Research Titled *Subject Protocol Registration* (SOP#: REGIST-101) must be followed.

**4.3 General Guidelines for Other Participating Institutions**

Eligible participants will be entered on study centrally at Massachusetts General Hospital by the Coordinating Center. All sites should contact the Coordinating Center to verify treatment availability prior to consenting a patient.

Following registration, participants may begin protocol treatment. Issues that would cause treatment delays should be discussed with the Principal Investigator/Sponsor. If a participant does not receive protocol therapy following registration, the participant's protocol status must be changed. The Coordinating Center should be notified of participant status changes as soon as possible.

**4.4 Registration Process for Other Participating Institutions**

To register a subject, the following documents should be completed by the participating institution and forwarded to the Coordinating Center:

- Copy of source documentation for all inclusion/exclusion criteria and screening procedures (See section 3 – Participant Selection and Section 9 – Study Calendar), including but not limited to:
  - Pathology confirming histology and stage
  - Echo or MUGA
  - Laboratories
  - PET CT report
- Demographics information
- Signed study consent form
- Study entry note documenting the informed consent process
- HIPAA authorization form, if applicable
- Eligibility checklist

The Coordinating Center will review the above documentation and contact the participating site to confirm eligibility. To complete the registration process, the Coordinating Center will:

- Register the participant on the study with QACT.
- Fax or e-mail the participant study number, and if applicable the dose treatment level, to the participating site.
- Call the participating site and verbally confirm registration, if necessary.

## 5. TREATMENT PLAN

This is a phase II trial of brentuximab plus AD (Adriamycin and Dacarbazine) for newly diagnosed, non-bulky, stage I or II classical Hodgkin Lymphoma. Treatment will be administered on an outpatient basis. Expected toxicities and potential risks as well as dose modifications for brentuximab/AD are described in Section 6 (Expected Toxicities and Dosing Delays/Dose Modification). No investigational or commercial agents or therapies other than those described below may be administered with the intent to treat the participant's malignancy. All protocol-specified treatments are +/- 3 days of the planned date, unless otherwise specified.

All participants will receive brentuximab/AD for 2 cycles followed by an interim restaging PET-CT scan. Patients in CR will receive 2 additional cycles of brentuximab/AD to complete a total of 4 cycles of therapy; patients with stable disease or partial response will receive 4 additional cycles to complete a total of 6 cycles. Patients with progressive disease will be taken off study. Brentuximab/AD will be administered on days 1 and 15 of each 28 day cycle. On treatment days, participants will receive brentuximab (1.2 mg/kg) followed by Adriamycin (25 mg/m^2 IV) and Dacarbazine (375 mg/m^2 IV).

Brentuximab vedotin will be administered prior to adriamycin and dacarbazine. Adriamycin and dacarbazine will be administered via institutional standards.

## 5.1 General Concomitant Medication and Supportive Care Guidelines

ABVD is routinely administered at full dose in the setting of neutropenia (see section 6 for dosing guidelines). This is in recognition that though neutropenia is common, the duration of neutropenia is short and fever and infectious complications are uncommon. Further, treatment delay and reduced dose intensity may impair treatment outcome. G-CSF is not routinely included in the care of these patients and thus will be used at the treating investigator's discretion in the setting of neutropenia, and may be used as prophylaxis for subsequent cycles if there is an episode of febrile neutropenia.

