We conducted a phase 2 study of 34 patients with non-bulky limited stage classical Hodgkin lymphoma, which completed accrual in 2014. Though data are immature, the treatment appeared highly effective and overall well tolerated. Preliminarily, all patients achieved complete response after 2 cycles of combination brentuximab-AD and no patients required more than 4 cycles of combination chemotherapy. One patient did relapse after achieving remission and was successfully treated with second-line therapy. One additional patient developed neutropenic sepsis and died in remission during therapy. An initially high rate of neutropenic fever was observed, prompting a protocol amendment requiring the use of GCSF support, after which the incidence of infection and neutropenic fever was much lower.

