Given these adverse late outcomes there have been efforts to de-escalate therapy with the hope of reducing toxicity while maintaining high cure rates. A strategy employing 4-6 cycles of ABVD (Adriamycin, Bleomycin, Vinblastine and Dacarbazine) with or without radiation in limited stage disease found no difference in overall survival between these groups at 5 years of follow-up. Analysis of this randomized trial at 12 years, however, demonstrated an improved overall survival in patients treated with 4-6 cycles of ABVD alone over combined modality therapy due to increased late events in patients treated with radiation. Chemotherapy alone yielded a favorable 12 year overall survival of 94%. Multiple other prospective and retrospective analyses have further validated ABVD chemotherapy alone in non-bulky limited stage cHL.

While a chemotherapy alone approach is appealing, the standard ABVD regimen is not without toxicity. Pulmonary toxicity from Bleomycin is the major non-hematologic toxicity of ABVD with incidence of pneumonitis ranging from 8-14%, and may result in treatment-related mortality. Neutropenia is also common, and may be worse when brentuximab vedotin is added to AVD, based on a high rate of neutropenic fever observed in our phase 2 trial prompting addition of routine growth factor support. We also observed a significant rate of peripheral neuropathy, likely related to the combination of vinblastine and brentuximab vedotin, both of which cause neuropathy due to activity on microtubules.

The German Hodgkin Study group explored whether Bleomycin and Dacarbazine are required to preserve the efficacy of this combination by comparing ABVD, AVB, AVD, and AV. In the final analysis, the omission of Dacarbazine resulted in a significantly inferior outcome, and omission of bleomycin also resulted in a slightly inferior PFS compared to AVD and ABVD. Another attempt to eliminate both bleomycin and dacarbazine in a phase II CALGB trial of AVG (Adriamycin, Vinblastine and Gemcitabine) in non-bulky limited stage patients, however, resulted in disappointing efficacy with a CR rate of 72.7% and 3-year PFS of 77%. These experiences suggest that a more potent anti-lymphoma therapy would need to be added in order to omit bleomycin with preserved efficacy.

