### 6.2.3 Hematologic Toxicity:

Blood counts should be checked on the day of or day before treatment. Hematologic guidelines are extrapolated from the accepted standard of care with ABVD, which is routinely administered at full dose in the setting of neutropenia, in the absence of fever. This is in recognition that though neutropenia is common, the duration of neutropenia is short and fever and infectious complications are uncommon. G-CSF is not routinely included in the care of these patients outside of the setting of febrile neutropenia or infections.

Blood Counts			Administer % of Full Dose
ANC (neutrophils+bands)		PLTs	Brentuximab, Adriamycin, Dacarbazine Dosing
≥500	And	≥50,000	100%
<500 and patient afebrile (temp <100.5 F)	And	≥50,000	100%. G-CSF support may be included at discretion of treating investigator.
<500 and patient febrile (temp ≥100.5 F)	Or	<50,000	Hold all chemotherapy and recheck within one week. Treatment of neutropenic fever per institutional guidelines. Restart at full dose on schedule or within one week after counts have rebounded to ANC ≥500 and PLT ≥75,000. G-CSF should be included for future cycles at treating physician's discretion. Treatment may be held for a maximum of 2 weeks, after which patients will be removed from study.

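### Sections 5.1 and 6.2.3 rest the discretionary G-CSF policy on ABVD experience and do not address the sponsor's own brentuximab-combination data in Sections 2.1 and 2.2

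*Combined protocol and SAP*

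**What the plan says.** The policy and its ground are in two places.

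- Section 5.1 opens with ABVD and says that "though neutropenia is common, the duration of neutropenia is short and fever and infectious complications are uncommon". It then concludes: "G-CSF is not routinely included in the care of these patients and thus will be used at the treating investigator's discretion". That discretion applies when neutropenia occurs. Prophylaxis for later cycles is mentioned as an option after an episode of febrile neutropenia.
- Section 6.2.3 names its source: "Hematologic guidelines are extrapolated from the accepted standard of care with ABVD". It repeats the ABVD premise and adds that "G-CSF is not routinely included in the care of these patients outside of the setting of febrile neutropenia or infections".

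The background describes the sponsor's own earlier phase 2 trial of 34 patients with the same disease.

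- Section 2.1: "An initially high rate of neutropenic fever was observed, prompting a protocol amendment requiring the use of GCSF support". Once that amendment was in force, both infections and neutropenic fever became much rarer. The section also reports: "One additional patient developed neutropenic sepsis and died in remission during therapy".
- Section 2.2 says that adding brentuximab to AVD may worsen neutropenia, and gives its reason: "based on a high rate of neutropenic fever observed in our phase 2 trial prompting addition of routine growth factor support".

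Section 2.1 calls the earlier regimen brentuximab-AD. Section 2.2 speaks of AVD and attributes the neuropathy seen to vinblastine together with brentuximab.

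**The concern.** A site reading Sections 5.1 and 6.2.3 is told that fever and infection seldom complicate the neutropenia it will see, and is given a G-CSF policy drawn from that statement. The statement describes a regimen without brentuximab. The only brentuximab-combination experience of the sponsor's own that the protocol reports on this question points the other way, and the policy sections are silent about it.

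The issue is a patient-safety premise. Section 2.2 puts cure rates in limited-stage disease above 85%, so an avoidable infectious death weighs heavily. The only numerical study-stopping rule, in Section 13.1.1, concerns response and not toxicity. The soundness of the stated premise therefore matters more than it would in a trial with a formal toxicity boundary.

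**Working it through.** The plan gives no figure on this point to reproduce. The check is a comparison of texts, plus one interval.

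**1. Is the ABVD premise the stated ground of the policy?** Yes. Section 5.1 moves from the ABVD experience to the discretionary policy with the word thus, and Section 6.2.3 says outright that its guidelines are extrapolated from ABVD.

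**2. Does either section cite brentuximab-combination evidence?** No. Neither mentions the earlier trial, its amendment, or the Section 2.3 hypothesis.

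**3. What does the earlier trial show, as reported?** Neutropenic fever was high at first, with no percentage. G-CSF became required by amendment, and infection and neutropenic fever were much lower afterwards. One patient developed neutropenic sepsis and died during therapy.

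**4. The one countable event.** Inputs from Section 2.1: x = 1, n = 34.

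- Proportion: 1/34 = 0.0294, or 2.9%.
- Exact (Clopper-Pearson) 95% lower limit: the 0.025 quantile of Beta(1, 34), which is 1 − 0.975^(1/34) = 0.0007, or 0.1%.
- Exact 95% upper limit: the 0.975 quantile of Beta(2, 33) = 0.1533, or 15.3%.

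The denominator pools patients treated before and after the amendment, and the date of the death relative to it is not given. The interval is therefore not an estimate of risk under either G-CSF policy. The more relevant quantity, the neutropenic fever rate, cannot be computed from the documents.

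**5. Which regimen produced these data?** There are two readings.

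- *Brentuximab-AD, as Section 2.1 writes.* The data would come from the regimen now under study, and the policy sections would be passing over direct evidence.
- *Brentuximab with AVD, as Section 2.2 implies.* This fits better. Section 2.2 invokes vinblastine, and Section 2.3 presents replacing vinblastine with brentuximab as the new step. The main bridge to this trial is then the Section 2.3 expectation of less neutropenia, which is put forward as a hypothesis and is not invoked in 5.1 or 6.2.3.

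**6. Does other evidence in the protocol close the gap?** Section 6.1.1 gives brentuximab monotherapy data: neutropenia of grade 3 or higher in 20% of patients, lasting a median of about one week, with only 3 of the grade 4 cases lasting 7 days or more. Its table of events of grade 3 or higher has no row for febrile neutropenia. These data are relevant but concern a single agent. They do not settle what happens when brentuximab is given with two other myelosuppressive drugs.

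Under either reading, the step from ABVD to this regimen is not supported where the policy is stated.

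**The case against.** The strongest reply is that nothing here is a contradiction. The sentence in Section 5.1 is about ABVD, and Section 6.2.3 says openly that it extrapolates. Fever can be uncommon with ABVD and frequent when brentuximab is added to AVD; both statements can be true. That stands. A reader might infer that the premise is refuted by the sponsor's own data, but the documents do not go that far. The defect is an extrapolation that is not justified in place.

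A reader might also infer that the sponsor saw these events with this very regimen. That rests on one name in Section 2.1, and Sections 2.2 and 2.3 make it look like a naming slip.

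The protocol also has safeguards. Section 6.2.3 allows G-CSF at the investigator's discretion when neutrophils are below 500 without fever, and holds all chemotherapy when they are below 500 with fever. Blood counts are taken at each treatment visit (Section 8.2). The monitoring committee reviews toxicity quarterly (Section 11.2). Grade 4 neutropenia is exempt from the additional reporting list in Section 10.4.1, but events meeting the SAE criteria are still reported. These safeguards limit the consequence of a poorly supported premise; they do not supply its support.

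Finally, a reader might argue that discretionary G-CSF will mask the reduction in neutropenia hypothesised in Section 2.3. That is too strong. The trial has one arm, neutropenia reduction is a rationale and not an endpoint, and Section 1.4 lists only the overall rate of grade III and IV events or discontinuation for toxicity. No neutropenia comparison is planned that could be masked.

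**Conclusion.** The concern holds as a gap between the policy sections and the background. Sections 5.1 and 6.2.3 carry an ABVD premise over to a brentuximab-containing regimen without addressing the sponsor's own combination trial, in which G-CSF became mandatory and infectious complications then fell.

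Its size cannot be put as a rate of neutropenic fever, because none is given. The one available number, 1/34 (2.9%, exact 95% CI 0.1% to 15.3%), shows that a death following neutropenic sepsis did occur, and little more. The verdict does not depend on that number or on which regimen name is correct. It assumes only that the background describes the earlier trial accurately in substance. It does not say which G-CSF policy is right.

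**What to change.** - Reconcile Sections 2.1, 2.2, 2.3, 5.1 and 6.2.3. The clinical team should base the policy in 5.1 and 6.2.3 on the brentuximab-combination evidence and not on ABVD alone. If the Section 2.3 hypothesis is part of the argument, the policy sections should say so and label it a hypothesis. No clinical rule is proposed here.
- Correct the name of the earlier regimen so that Sections 2.1 and 2.2 agree. If available, add its neutropenic fever rate before and after the amendment and the timing of the death.
- For the analysis, at most report overall rates of febrile neutropenia and of infection of grade 3 or higher, with the proportion receiving G-CSF and when it was started, as description only. A table of these events split by G-CSF use should not be added: G-CSF is given in response to neutropenia or febrile neutropenia, so users would show more events because the events led to use.

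The cost is a wording amendment reviewed by the clinical team and a few lines in the safety report. Section 8 has concurrent medications recorded at visits, but the form list in Section 11.1.2 names no concomitant-medication form, so confirm that G-CSF use and dates reach the database.
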